4 STUDY PROCEDURES

4.1 Home Monitoring

Subjects will record their PIFR using the InCheck DIAL® and modified Borg dyspnea score three times weekly (MWF) when clinically stable and daily while respiratory symptoms worsen per patient self-assessment. At each session, the participant will repeat efforts three times, with the highest of the three repeated efforts being recorded by the participant. They will be asked to perform the PIFR for the DPI(s) they are receiving at home (Ellipta®, Inhub®, Diskus® or Handihaler®) using the InCheck DIAL®. If on more than one DPI, patient will record PIFR for each device. PIFR will be recorded with best approximation to nearest 1 L/min.

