- Patient-reported outcomes (PROs)
 - CAT score (COPD Assessment test)
 - mMRC score (modified Medical Research Council)
 - mBorg score (modified Borg dyspnea score)

- PIFR measurement in three different physical positions – sitting, standing, and lying tilted at 45° with head forward. (repeated using PIFR setting for each DPI patient is receiving)
- Pre- and post-bronchodilator PIFR measurement in sitting position
- Subject instructed on proper use of PIFR device and recording of PIFR measurement and modified Borg dyspnea score using the provided Study Notebook
- Subject instructed to mail PIFR and modified Borg dyspnea score on a monthly basis to the research team using supplied self-addressed, stamped envelopes

Visits 3, 4, 5, and 6 - Telephone Visits

At Visits 3, 4, 5, and 6 (at 4, 8, 12 , and 24 weeks after Visit 2 -permissible ± 2 week window for each visit), study personnel will contact the participant by telephone to obtain PIFR and symptom questionnaires recordings during the preceding 2 weeks. A time period less than 2 weeks is acceptable if the subject had mailed in their monthly log recently. PIFR measurements and respiratory symptom questionnaires (modified Borg dyspnea score only) will have been recorded by study participants using a Study Notebook. PIFR will be recorded for each DPI the patient is receiving. A CAT score, mBorg, and mMRC will also be determined by study personnel as part of each visit. Ascertainment of exacerbations, medication adherence, and change in inhaler regimens will be completed. In part, the telephone visit will be undertaken to increase subject's compliance to study procedures.

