6 STATISTICAL CONSIDERATION

6.1 Primary Endpoint

For each patient the occurrence of suboptimal Peak Inspiratory Flow Rate (sPIFR) over 24 weeks. sPIFR will be defined as any two consecutive measurements on different days below the optimal threshold for any prescribed DPI (e.g., <30 L/min for Handihaler® (High resistance DPI), <60 L/min for Ellipta® (Medium resistance DPI))

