- We will use mixed models to explore associations of monthly PIFR averages over time and clinical and demographic factors. Subjects will be considered as random factor, other variables will be considered fixed effects.
- Association of PIFR with CAT score, mBORG score and mMRC
 - Association of PIFR and CAT scores at V1, V3, V4, V5, V6 (for PIFR, use the measurement in the week of each telephone follow-up, or the month average)

- Correlation of change in CAT scores with change in PIFR from baseline after 24 weeks
- Association of PIFR and mBORG score at V2, V3, V4, V5, V6
- Association of PIFR and mMRC scores at V1, V3, V4, V5, V6 (for PIFR, use the measurement in the week of each telephone follow-up, or the month average)

For COPD exacerbation analyses, the proportion of patients with COPD exacerbations (from Kaplan Meier curve) and the rate of exacerbations occurring during follow-up will be reported along with 95% CI. A patient will be considered censored for exacerbations at the time of the last documented visit, the end of the study, the switching of device (between medium and high resistance DPI) or death (whichever occurs earlier), if they did not experience an exacerbation before. The exacerbations will be reported overall and stratified by severity. The associations between exacerbations and PIFR will be explored in different ways, for all exacerbation, stratified by severity of exacerbations, and stratified by device.

- The rate of exacerbations and sPIFR will be analyzed with negative binomial models (or another model if more appropriate).
- For patients with exacerbations, the mean of PIFR in the week before, of, and after each exacerbation will be calculated and reported.

All tests with p value < 0.05 will be interpreted nominally as statistically significant.

Missing data

- No imputation for PIFR
- No imputation for COPD exacerbations
- No imputation for CAT, mBORG and mMRC

Sample Size and Power

In this application, we propose to recruit 120 COPD participants for study enrollment. There are several rationales for this sample size selection.

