16 APPENDIX 1. STUDY PROCEDURES AND ASSESSMENTS

Visit number	V1 ^a	V2	V 3,4,5,6
Procedures and assessments	Screening Visit	Enrollment Visit	Telephone Follow-up Visits
Target time(s) and allowable time frames		At same time as or within 1 month of Screening Visit	At 4, 8, 12, 24 weeks after V2 (± 2 weeks)
Informed consent	X		
Clinical history	X	X	
Prior medication history	X	X	
Inclusion and exclusion criteria	X	X	
Physical examination including waist circumference		X	
Vital signs measurement		X	
Peak Inspiratory Flow Rate (Performed in triplicate at resistance of all DPIs the patient is receiving)	X	Pre- and post-bronchodilator (albuterol) Perform PIFR in three positions (sitting, standing, and lying at 45° angle with head tilted forward) [#]	Done 3x/wk. (each session in triplicate with highest value recorded) at home by patient after enrollment [#] (Daily during worsened symptoms)
COPD Assessment Test score (CAT) questionnaire	X	X	X
Modified Borg Dyspnea Score (mBorg)		X	X Done 3x/wk at home by patient after enrollment
Modified Medical Research Council questionnaire (mMRC)		X	X
COPD exacerbation history*	X	X	X
COPD medication use and adherence	X	X	X

^aMild, moderate and severe exacerbations will be defined as:

Mild – doubling use of inhaled rescue medication ≥ 48 hours and not meeting definition of moderate or severe; Moderate – increased rescue medication and oral corticosteroid, not requiring hospitalization; Severe – hospitalization for exacerbation

[figure not shown]
PIFR will be performed before performing spirometry (if spirometry is performed at that visits) using InCheck Dial settings for each DPI patient is receiving

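### The telephone back-up for unmailed home PIFR logs looks back only two weeks and no notebook return is required, so gaps in the readings can hide primary-endpoint events

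*Combined protocol and SAP*

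**What the plan says.** Section 6.1 sets the endpoint: "sPIFR will be defined as any two consecutive measurements on different days below the optimal threshold for any prescribed DPI", counted per patient over 24 weeks. Section 4.1 has patients measure at home "three times weekly (MWF) when clinically stable and daily while respiratory symptoms worsen per patient self-assessment".

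Section 4.2 gives two routes by which these readings reach the team.

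- **Mail (main route).** At Visit 2: "Subject instructed to mail PIFR and modified Borg dyspnea score on a monthly basis to the research team", with stamped envelopes supplied.
- **Telephone (back-up).** Visits 3 to 6 fall, in Appendix 1, "At 4, 8, 12, 24 weeks after V2", each with a two-week window either side. Staff call "to obtain PIFR and symptom questionnaires recordings during the preceding 2 weeks". The one stated adjustment is downward: "A time period less than 2 weeks is acceptable if the subject had mailed in their monthly log recently".

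Under 4.2 every contact after enrollment is by telephone, and 4.3 rules out unscheduled visits. No section asks for the notebook back or sets a procedure for an overdue log. Section 6.3 states "No imputation for PIFR". It takes the primary proportion from a Kaplan-Meier curve, censoring at the latest documented visit or PIFR measurement, end of study, switch of device resistance class or death. It does not say how gaps inside a patient's series are handled.

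**The concern.** The back-up works in the wrong direction. It can be cut short when the mailed log has arrived and the call adds little, and it is not extended when the log is missing and the call is the only source. Readings already taken may then stay in the patient's notebook.

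Two low readings on different days make an event. If they fall in an uncollected stretch and later data arrive, the patient remains in the Kaplan-Meier risk set as though no event had occurred. That is bias, not imprecision: a larger sample does not remove it, and the confidence interval does not show it. Nor does the plan ask for a completeness figure from which a reader could judge it.

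**Working it through.** **1. The plan's own figure.** The sample-size table uses n = z² p(1−p)/d². With p = 0.40, d = 0.088 and z = 1.96: 3.8416 × 0.24 / 0.007744 = 119.06, rounded up to 120, as stated. All 15 cells reproduce. The sample size is not in question.

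**2. Coverage by calls alone.** Scheduled sessions per device: 24 weeks × 3 = 72 (more if symptoms worsen). Calls: 4 × 2 weeks = 8 weeks, so 8 × 3 = 24 sessions, or 24/72 = 33%. Moving the calls within their windows left the total at 24 in the two shifted schedules tried. At nominal timing:

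| Unmailed 4-week log | Sessions due | Recovered by call |
|---|---|---|
| Month 1, 2, 3 or 6 | 12 | 6 |
| Month 4 or 5 | 12 | 0 |
| All six | 72 | 24 |

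Months 4 and 5 get nothing because no call falls between weeks 12 and 24; weeks 13 to 22 are uncovered.

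**3. Effect on the event proportion among affected patients.** Inputs from the documents: pilot PIFR at Diskus resistance 61 ± 13 L/min (1.3), eligibility 60 to 90 L/min (3.4), threshold 60 L/min, 72 readings. Assumed: a stable patient mean, independent readings around it, and a within-person SD of 3, 5 or 7 L/min. Every simulated patient is followed to week 24, so the crude and Kaplan-Meier proportions coincide.

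| Within-person SD | All 72 readings | Calls only | Loss |
|---|---|---|---|
| 3 | 22% | 16% | 6 points |
| 5 | 38% | 29% | 9 points |
| 7 | 56% | 44% | 12 points |

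The levels shift with how eligibility is applied. At SD 5, a variant that screens on the observed baseline gives 39% versus 30%, again 9 points. These runs let low readings on either side of a gap count as consecutive; disallowing that gives 16%, 28% and 42% for calls only.

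For partial non-mailing at SD 5, with all calls completed, one missed log costs about 0.7 points (months 1, 2, 3 or 6) or about 1.3 to 1.5 (month 4 or 5). Missing months 4 and 5 together costs about 3.

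**4. Effect on the overall estimate.** Overall loss = share affected × loss among affected. With an assumed 20 to 40% affected at SD 5:

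- one missed log: 0.20 × 0.7 = 0.1 to 0.40 × 1.5 = 0.6 points;
- months 4 and 5 both missed: 0.20 × 3 = 0.6 to 0.40 × 3 = 1.2 points;
- never mailing: 0.20 × 9 = 1.8 to 0.40 × 9 = 3.6 points.

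**5. A different event model.** Suppose a true 40% of patients have one continuous low spell starting at a random time. For spells of 1, 2, 4 or 8 weeks, calls alone detect 34%, 49%, 65% or 81% of events. Observed proportion = 0.40 × (1 − m(1 − d)), where m is the share never mailing and d the detection rate. With m = 0.20 and a 1-week spell: 0.40 × (1 − 0.20 × 0.665) = 35%. For 2, 4 and 8 weeks the results are 36%, 37% and 39%. Short spells are the most easily missed.

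**The case against.** Mailing is the main route and covers all 24 weeks. The two-week rule governs what a call obtains; it does not refuse late logs or stop staff asking for one. Section 4.2 says the calls are partly meant to raise compliance, and Section 8 has staff review collection forms for completeness as they go. A reader might infer that unmailed readings are lost by design; the documents do not support that. Still, both safeguards are general, neither mentions an overdue log, and reviewing forms received does not recover pages never sent. Section 5.1.2 lists Visit 6 among clinic visits, which might suggest the notebook is handed in then, but 4.2 and Appendix 1 make it a telephone visit and no section has the notebook collected.

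A reader might also infer that every lost week counts as event-free. Under 6.3 that holds only for a gap followed by later documented data. Where a patient's data stop, as with a missing final log and nothing documented after it, the patient is censored earlier, which biases the estimate only if missingness relates to PIFR. Nor is the direction strictly one-way: the definition sets no maximum interval between consecutive readings, so isolated low readings on either side of a gap could pair. In the simulation this did not reverse the direction.

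A third inference, that sicker patients mail less and the bias therefore falls on those most likely to have events, is conjecture; no passage links mailing to severity.

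Finally, the larger figures describe patients who mail none of six logs, and even an overall loss of 2 to 4 points is below the planned half-width of 8.8. That stands as a limit on size. It does not answer the point that the loss is a bias.

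**Conclusion.** The point holds as a weakness in the collection rule. For an overdue log the written back-up recovers half the scheduled sessions, or none in months 4 and 5. Gaps followed by later data then hide events from the primary estimate, mainly downward.

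The size is small to moderate and cannot be fixed from the documents, which give neither the mailing rate nor the within-person SD. At an assumed SD of 5 L/min, affected patients lose about 0.7 to 1.5 points for one missed log, about 3 for months 4 and 5 together, and about 9 if they never mail. It would be tempting to quote 2 to 4 points as the expected overall bias, but that needs 20 to 40% of patients never to mail anything, a rate the documents do not give. Occasional missed logs cost well under that. The change is worth making because it is cheap and unreturned notebooks may be hard to recover after the study closes.

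**What to change.** - In 4.2, replace the two-week look-back with all readings since the last log received. Where the backlog is long, request the overdue pages by mail instead of dictation.
- Require return of the notebook at week 24 in a pre-paid envelope; envelopes are already supplied for the monthly logs.
- Report sessions received against sessions expected, per patient.

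No visit or measurement is added. The cost is some longer calls or an extra mailing for patients with overdue logs. Dictation alone would be burdensome in the worst case: with nothing received since week 12, the week-24 call would cover 12 × 3 = 36 sessions. For a patient on two DPIs that is 36 × 3 = 108 values (two PIFR and one Borg each), with a risk of transcription error. Hence the mail option.

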4.3 Unscheduled visits

No unscheduled visits will be incorporated into this protocol.

4.4 Concomitant Medication documentation

All COPD medications within 30 days of study enrollment and during the 24 week study period will be recorded.

4.5 Rescue medication administration (if applicable)

Inhaled albuterol 2 puffs by metered dose inhaler will be administered as part of pre- and post-PIFR measurement at Visit 2

4.6 Subject Completion/ Withdrawal procedures

If a patient decides to withdraw for any reason our contact information will be provided and they can email any member of the research team. If participants have a change in their prescribed DPI during study, study procedures will continue using previously prescribed DPIs and noting prescription changes.

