6.3 Statistical Methods

Analysis populations

Full analysis set (FAS): all screened patients with informed consent and at least two consecutive PIFR measurements on different days.

Descriptive Statistics

Using the FAS, the following variables will be described using descriptive statistics (mean and standard deviation, min, max, median) and graphical displays (boxplots, histograms). Data transformation will be used if applicable, and extreme values will be verified and their effect on analysis results will be reported.

- demographics and clinical variables
- patient reported outcomes (CAT, mBORG and mMRC)
- concomitant diseases and medications

Primary analysis

The primary endpoint will be described as the proportion of patients with suboptimal PIFR and reported with 95% confidence intervals, on the FAS. The proportion of sPIFR will be computed from the Kaplan-Meier curve.

Subgroup analyses of the primary endpoint:

- per DPI device type (moderate vs. high resistance)
- per gender
- per GOLD stage based on spirometry results.

Analysis of exploratory endpoints: on FAS.

We will analyze the PIFR measurements over time, specifically:

- Descriptive analysis of PIFR measurements, including mean (SD), median (IQR), range over time per patient per device, and in different body positions (standing, sitting, supine at 45 degrees). PIFR curves per patient/device can be explored. Descriptive analysis for different time's period (week, month) may be explored.
- The time of first occurrence of sPIFR will be reported in days and will be plotted with a Kaplan-Meier curve. A patient will be considered censored for sPIFR at the time of the latest documented visit or PIFR measurements, the end of the study, the switching of device (between medium and high resistance DPI) or death (whichever occurs earlier), if they did not experience a sPIFR before. Associations with possible demographics and clinical variables will be explored using a Cox regression analysis.
- The proportion of suboptimal PIFR measurements will be reported with 95% CI, and also the rates. This analysis will also be performed per device in patients that used two devices with different resistances (e.g. Advair + Spiriva HH).
- We will explore, for each device, with logistic regression (binary) or negative binomial (count) the clinical and demographic factors associated with sPIFR measurements.

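### After a DPI change, the measurement, event and censoring rules follow different devices, so the primary proportion fits neither an enrolment-device nor a while-prescribed target

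*Combined protocol and SAP*

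**What the plan says.** - **Measurement after a change.** Section 4.6 covers any change of DPI: "If participants have a change in their prescribed DPI during study, study procedures will continue using previously prescribed DPIs and noting prescription changes".
- **Routine measurement.** Section 4.1 says of home sessions: "They will be asked to perform the PIFR for the DPI(s) they are receiving at home". Section 4.2 says of the telephone visits: "PIFR will be recorded for each DPI the patient is receiving". Section 5.1.4 and Appendix 1 use the same present tense.
- **Event.** Section 6.1: "sPIFR will be defined as any two consecutive measurements on different days below the optimal threshold for any prescribed DPI". The Synopsis repeats this under the endpoint and again under the statistical plan. None of the three places says whether a DPI must be prescribed at enrolment or on the day of the reading.
- **Censoring.** Among the censoring reasons for sPIFR, Section 6.3 lists "the switching of device (between medium and high resistance DPI) or death (whichever occurs earlier), if they did not experience a sPIFR before". It repeats the device-switch reason for exacerbations.
- **Link to the primary result.** The censoring rule is written under the exploratory time-to-event analysis, but Section 6.3 says of the primary analysis: "The proportion of sPIFR will be computed from the Kaplan-Meier curve". It is the only sPIFR censoring rule in the plan, so it governs the primary proportion.

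No rule covers stopping a DPI for an MDI or Respimat, adding a second DPI, dropping one of two, or changing within a resistance class.

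**The concern.** Two targets would be coherent. One is PIFR at the setting of the enrolment DPI over 24 weeks, whatever is prescribed later. The other is PIFR on a DPI for as long as it is prescribed. Section 4.6 collects data for the first. The censoring rule moves towards the second, but for only one kind of change. What a patient contributes to the primary proportion after a change therefore depends on which inhaler came next.

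If the reason for a class switch is related to falling PIFR, censoring at the switch is informative: Kaplan-Meier gives the censored patient the average remaining risk, and the proportion is too low. The confidence interval would not show this. Leaving the reference date of *prescribed* open also means someone must decide, possibly after seeing the data, whether readings at a stopped DPI's setting count.

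**Working it through.** **1. The plan's own figure.** The precision table in Section 6.3 follows n = z²p(1−p)/d². At p = 0.40 and d = 0.088, n = 1.96² × 0.24 / 0.088² = 119.05, rounded up to 120. All 15 cells reproduce. At N = 120 and p = 0.40 the half-width is 1.96 × √(0.24/120) = 8.8 points.

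**2. The rules applied to four kinds of change.**

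| Change | Setting measured under 4.6 | Censored under 6.3? | Can later readings be primary events? |
|---|---|---|---|
| Ellipta replaced by Handihaler | Ellipta | Yes | No, although they are collected |
| Handihaler replaced by Respimat or an MDI | Handihaler | No | Yes if *prescribed* means at enrolment. No if it means currently, and the patient then stays at risk with no event possible |
| Handihaler added to Ellipta | Ellipta; Handihaler unclear | Not clearly a switch | On Handihaler, only if it is measured: yes if 4.1 and 4.2 govern, no if an addition is a change under 4.6 |
| Diskus replaced by Ellipta | Diskus | No | Same resistance class and same 60 L/min threshold, so little turns on it |

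An enrolment-device target would keep following the patient in rows 1 and 2. A while-prescribed target would stop in both. The plan stops in row 1 and continues in row 2.

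**3. Possible size.** The documents give neither a switching rate nor reasons for switching, so everything here is assumed:
- 24-week risk of 40% in non-changers (the pilot figure in Section 6.3), constant hazard.
- A share s of patients would change DPI at week 12 if still event-free.
- Changers' hazard is equal to, or twice, that of others throughout.

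Let a be the 12-week event-free probability in non-changers and c that in changers. Then a = √0.6 = 0.775. With doubled hazard, c = 0.6.

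- Later readings counted: 1 − [(1−s)a² + sc²]
- Censored at the change: 1 − [(1−s)a + sc] × a
- At risk with no later event possible: 1 − [(1−s)a² + sc]
- Counted minus censored: s × c × (a − c). This is zero when c = a, and s × 0.6 × 0.175 with doubled hazard.

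| Hazard in changers | s | Counted | Censored | At risk, none counted |
|---|---|---|---|---|
| Equal | 5% | 40.0% | 40.0% | 39.1% |
| Equal | 10% | 40.0% | 40.0% | 38.3% |
| Equal | 20% | 40.0% | 40.0% | 36.5% |
| Doubled | 5% | 41.2% | 40.7% | 40.0% |
| Doubled | 10% | 42.4% | 41.4% | 40.0% |
| Doubled | 20% | 44.8% | 42.7% | 40.0% |

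With doubled hazard, censoring lowers the estimate by 0.5, 1.0 and 2.1 points. The last column is the effect of reading *prescribed* as current if every changer stopped to a non-DPI inhaler. It differs from the counted column even at equal hazard.

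**4. Precision.** With every changer censored and doubled hazard, the Greenwood half-width at N = 120 is 8.9, 9.0 and 9.3 points at s = 5%, 10% and 20%. At equal hazard and s = 20% it is 9.4. The target of under 10 points is still met.

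**The case against.** Several counter-arguments have force.

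- **Section 4.6 is the specific rule and the others are the default.** This is fair and probably what was meant. It settles much of the measurement conflict, but not the event definition or the censoring.
- **Collecting beyond a censoring time is not a contradiction.** This stands. A reader might infer that post-switch readings are thrown away. They are not: they remain available for the per-device descriptions, the mixed models of monthly averages and the 24-week change correlation. They are lost only to the time-to-event curve and hence to the primary proportion.
- **Stopping at a class switch is a defensible on-device choice**, since the objective concerns patients receiving DPIs. This stands for that change taken alone. The same logic would end follow-up when a DPI is stopped for a non-DPI inhaler, and the plan does not do that.
- **An added DPI may well be measured.** A reader might infer from Section 4.6 that it never is. The text does not establish that, because an addition need not be a change of DPI. It is an ambiguity, not a certain loss of events.
- **Informative censoring is not shown.** This stands. Section 1.3 says the cohort was chosen because its PIFR may approach the minimum with worsened symptoms, and Section 3.2 says nothing is blinded, so a link between low readings and switching is plausible. But no passage gives reasons for switching, and with daily readings during worsening some declining patients would have their event first.
- **The reverse choice of primary and sensitivity analysis is equally coherent.** This is true. The defect requires one rule. The enrolment-device rule is preferred here because its data are already to be collected.

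**Conclusion.** The inconsistency is certain on the text, and it reaches the primary result through the Kaplan-Meier curve. It should be corrected before analysis. Its numerical effect is unknown and may be nil: censoring bias is zero if class switching is unrelated to PIFR, and about 0.5 to 2.1 points downward for 5% to 20% changers under the doubled-hazard illustration, against a half-width of 8.8 points. The sample size is not in question.

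A reader might infer that the primary proportion will be substantially too low. That needs assumptions the documents do not supply. For instance, a remaining risk of 40% to 60% after week 12, against 22.5% (1 − √0.6) for others, implies hazard ratios of ln 0.6 / ln 0.775 = 2.0 to ln 0.4 / ln 0.775 = 3.6. If 15% of all patients (18 of 120) were event-free at week 12 and all changed class then, the shortfall would be 0.15 × (0.40 − 0.225) = 2.6 to 0.15 × (0.60 − 0.225) = 5.6 points. Nothing in the plan supports that rate or those ratios. Confidence is high for the mismatch of rules, not for the direction or size of any bias.

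**What to change.** Use one rule for every DPI change.

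1. **Endpoint.** In Section 6.1 and both Synopsis entries, count low readings on any DPI prescribed at enrolment. State that a DPI added later does not contribute to the primary endpoint.
2. **Primary analysis.** In Section 6.3, remove the device-switch censoring for sPIFR and use the Section 4.6 readings to week 24.
3. **Sensitivity analysis.** End follow-up for a device when it is no longer prescribed, whatever replaced it.
4. **Data.** Record the date of each prescription change. The plan notes changes (Section 4.6), asks about them at the telephone visits (Section 4.2) and records COPD medications (Section 4.4), but does not say that dates are captured.
5. **Alignment.** Bring Sections 4.1, 4.2 and 5.1.4 and Appendix 1 into line with Section 4.6, and check the matching exacerbation censoring rule in Section 6.3 for consistency.

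The cost is protocol and SAP wording plus one date field. There are no extra patients or visits, and patients' inhaler treatment is not touched. The downside is that some primary readings will come from a device setting the patient no longer uses, and low flow on a newly added DPI will not be counted. The sensitivity analysis shows the effect of the first but not of the second.
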